APPENDIX 3. SAS CODE FOR PRIMARY EFFICACY ANALYSIS

Definition	Variable
Subject number (character)	SUBJID
Planned double-blind treatment group (numeric)	TRT01PN (1=" SEP-36385 25, 50 or 75 mg/day"; 2="Placebo")
Visit (numeric)	AVISITN (4="Week 2"; 5="Week 3"; 6="Week 5"; 7="Week 6")
Change from baseline values (numeric)	CHG
Baseline values (numeric)	BASE
SAPS-PD total score at each post-baseline visit	SAPS-PD 4 to SAPS-PD 7

Mixed Model for Repeated Measures (MMRM)

```

ODS OUTPUT LSMEstimates=xxxx Coef=xxxx;
PROC MIXED DATA=xxxx;
  CLASS SUBJID TRT01PN AVISITN;
  MODEL CHG = <Baseline SAPS-PD total score> TRT01PN AVISITN TRT01PN *AVISITN /
  DDFM=KR SOLUTION;
  REPEATED AVISITN /SUB=SUBJID TYPE=UN;
  LSMESTIMATE TRT01PN *AVISITN "SEP-363856 at Week 2" [1, 2 1],
    "SEP-363856 at Week 3" [1, 2 2],
    "SEP-363856 at Week 5" [1, 2 3],
    "SEP-363856 at Week 6" [1, 2 4] / E CL;

  LSMESTIMATE TRT01PN *AVISITN "Placebo at Week 2" [1, 1 1],
    "Placebo at Week 3" [1, 1 2],
    "Placebo at Week 5" [1, 1 3],
    "Placebo at Week 6" [1, 1 4] / E CL;

  LSMESTIMATE TRT01PN *AVISITN
    "SEP-363856 vs Placebo at Week 2" [1, 2 1] [-1, 1 1],

```

Document: \

Author:

Version Number:
Version Date:

Final 1.0
24FEB2020

Template No: CS_TP_BS016 Revision 4
Effective Date: 01Apr2016

Reference: CS_WI_BS005

"SEP-363856 vs Placebo at Week 3" [1, 2 2] [-1, 1 2],
"SEP-363856 vs Placebo at Week 5" [1, 2 3] [-1, 1 3],
"SEP-363856 vs Placebo at Week 6" [1, 2 4] [-1, 1 4] / E CL;

RUN;

Pattern-Mixture Model (PMM) with Placebo-Based MI

Step 1: Partial imputation to get monotone missing pattern:

```
PROC MI DATA=xxxx SEED=12345 NIMPUTE=1000 OUT=xxxx_mono;  
  MCMC CHAIN=MULTIPLE INITIAL=EM IMPUTE=MONOTONE NBITER=5000 NITER=200;  
  VAR TRT01PN <Baseline SAPS-PD total score>;  
RUN;
```

Step 2: Impute with monotone method:

```
PROC MI DATA=xxxx_mono SEED=12345 NIMPUTE=1 OUT=xxxx_imp;  
  VAR <Baseline SAPS-PD total score>;  
  CLASS TRT01PN ;  
  MNAR model (SAPS-PD4/model0bs=(TRT01PN='1'));  
  MNAR model (SAPS-PD5/model0bs=(TRT01PN='1'));  
  MNAR model (SAPS-PD6/model0bs=(TRT01PN='1'));  
  MNAR model (SAPS-PD7/model0bs=(TRT01PN='1'));  
  MONOTONE REG;  
  BY _Imputation_;  
RUN;
```

Step 3: Derive change from baseline at all visits, then fit the primary MMRM on each imputed dataset:

```
ODS OUTPUT LSMEstimates=LSMEST;  
PROC MIXED DATA=xxxx_imp;  
  CLASS SUBJID TRT01PN AVISITN;  
  MODEL CHG = <Baseline SAPS-PD total score> TRT01PN AVISITN TRT01PN *AVISITN /  
  DDFM=KR SOLUTION COVB;  
  REPEATED AVISITN /SUB=SUBJID TYPE=UN;  
  LSMESTIMATE TRT01PN *AVISITN "SEP-363856 at Week6"  
    [1, 1 4] / E CL;
```

Document: \

Author:

Version Number:
Version Date:

Final 1.0
24FEB2020

Template No: CS_TP_BS016 Revision 4
Effective Date: 01Apr2016

Reference: CS_WI_BS005

LSMESTIMATE TRT01PN *AVISITN "Placebo at Week 6"

[1, 2 4] / E CL;

LSMESTIMATE TRT01PN *AVISITN "SEP-363856 vs Placebo at Week 6"

[1, 1 4] [-1, 2 4] / E CL;

BY _Imputation_;

RUN;

Step 4: Combine results using Rubin's imputation rules:

PROC MIANALYZE parms(classvar=full)=LSMEST;

CLASS TRT01PN *AVISITN;

MODELEFFECTS TRT01PN *AVISITN;

ODS OUTPUT ParameterEstimates=mianLSMEST;

RUN;

Tipping Point Analysis

Step 1: Impute non-monotone missing data using step 1 from above Pattern Mixture Model (PMM) with Placebo-Based MI.

Step 2: Impute the remaining missing data using a MAR-based regression model, and add a value delta to all imputed values in the SEP-3638528 25, 50 or 75 mg/day group:

PROC MI DATA=xxxx_mono seed=12345 NIMPUTE=1 out=xxxx_imp;

VAR TRT01PN <Baseline SAPS-PD total score>;

CLASS TRT01PN ;

MONOTONE REG;

MNAR adjust (SAPS-PD4/delta=xx adjustobs=(TRT01PN ='1')) ;
MNAR adjust (SAPS-PD5/delta=xx adjustobs=(TRT01PN ='1')) ;
MNAR adjust (SAPS-PD6/delta=xx adjustobs=(TRT01PN ='1')) ;
MNAR adjust (SAPS-PD7/delta=xx adjustobs=(TRT01PN ='1')) ;

BY _Imputation_;

RUN;

Step 3: Repeat steps 3 and 4 from above Pattern Mixture Model (PMM) with Placebo-Based MI to analyze the multiply imputed and shifted (by delta) data, and to combine the results using Rubin's imputation rules.

Document:

\

Author:

Version Number:

Final 1.0

Version Date:

24FEB2020

Template No: CS_TP_BS016 Revision 4
Effective Date: 01Apr2016

Reference: CS_WI_BS005

**APPENDIX 4. STEP 4: REPEAT STEP 2 AND 3 ABOVE FOR ALL VALUES OF
DELTA. POTENTIALLY CLINICALLY SIGNIFICANT (PCS) LABORATORY
CRITERIA**

Category	Parameter Name	PCS Low	PCS High
	Age/Gender Restriction, if any		
HEMATOLOGY			
WBC	$\leq 2.8 \times 10^9/L$	$\geq 16 \times 10^9/L$	
Neutrophils (abs)	$< 0.5 \times 10^9/L$	$> 13.5 \times 10^9/L$	
Lymphocytes (abs)	N/A	$> 12 \times 10^9/L$	
Monocytes (abs)	N/A	$> 2.5 \times 10^9/L$	
Eosinophils (abs)	N/A	$> 1.6 \times 10^9/L$	
Basophils (abs)	N/A	$> 1.6 \times 10^9/L$	
Neutrophils (relative)	≤ 0.15	> 0.85	
Lymphocytes (relative)	N/A	≥ 0.75	
Monocytes (relative)	N/A	≥ 0.15	
Eosinophils (relative)	N/A	≥ 0.10	
Basophils (relative)	N/A	≥ 0.10	
Hemoglobin			
Male	$\leq 115 \text{ g/L}$	$\geq 190 \text{ g/L}$	
Female	$\leq 95 \text{ g/L}$	$\geq 175 \text{ g/L}$	
Hematocrit			
Male	≤ 0.37	≥ 0.60	
Female	≤ 0.32	≥ 0.54	
RBC	$\leq 3.5 \times 10^{12}/L$	$\geq 6.4 \times 10^{12}/L$	
Platelet Count	$\leq 75 \times 10^9/L$	$\geq 700 \times 10^9/L$	
Ery. Mean Corpuscular Volume (fL)	≤ 70	≥ 110	
SERUM CHEMISTRY			
Sodium	$< 130 \text{ mmol/L}$	$> 150 \text{ mmol/L}$	
Potassium	$< 3 \text{ mmol/L}$	$> 5.5 \text{ mmol/L}$	
Chloride	$\leq 90 \text{ mmol/L}$	$\geq 118 \text{ mmol/L}$	
Calcium	$< 1.75 \text{ mmol/L}$	$\geq 3.1 \text{ mmol/L}$	
Phosphate	$< 0.65 \text{ mmol/L}$	$> 1.65 \text{ mmol/L}$	
Bicarbonate	$< 15.1 \text{ mmol/L}$	$> 34.9 \text{ mmol/L}$	
Magnesium	$< 0.4 \text{ mmol/L}$	$> 1.23 \text{ mmol/L}$	
AST (IU/L)	N/A	$\geq 3 \times \text{ULN}$	
ALT (IU/L)	N/A	$\geq 3 \times \text{ULN}$	
Alkaline Phosphatase (IU/L)	N/A	$\geq 1.5 \times \text{ULN}$	
CK (IU/L)	N/A	$> 2.5 \times \text{ULN}$	
Creatinine	N/A	$\geq 177 \text{ umol/L}$	
BUN	N/A	$\geq 10.7 \text{ mmol/L}$	

Document:

\

Author:

Version Number:

Final 1.0

Version Date:

24FEB2020

Template No: CS_TP_BS016 Revision 4
Effective Date: 01Apr2016

Reference: CS_WI_BS005

Direct Bilirubin	N/A	> 2 x ULN
Indirect Bilirubin	N/A	> 2 x ULN
Bilirubin (mg/dL)	N/A	≥ 34.2 umol/L OR > 2 x ULN
Protein	≤ 45 g/L	≥ 100 g/L
Albumin	≤ 25 g/L	N/A
Cholesterol	N/A	> 7.76 mmol/L
HDL-Cholesterol	< 0.78 mmol/L	N/A
LDL-Cholesterol	N/A	> 4.14 mmol/L
Triglycerides	N/A	> 3.42 mmol/L
Uric acid		
Male	N/A	> 595 umol/L
Female	N/A	> 476 umol/L
Glucose	< 2.78 mmol/L	> 13.9 mmol/L
HbA1c	N/A	≥ 0.075
Prolactin (Male and Female)	N/A	≥ 5 x ULN
COAGULATION		
aPTT (sec)	N/A	> 1.5 x ULN
INR (ratio)	N/A	> 1.5 x ULN
PT (sec)	N/A	> 1.5 x ULN
URINALYSIS		
RBC	N/A	> 25 hpf
WBC	N/A	> 25 hpf

Document:

\

Author:

Version Number:

Final 1.0

Version Date:

24FEB2020

Template No: CS_TP_BS016 Revision 4
Effective Date: 01Apr2016

Reference: CS_WI_BS005

Document Approval Signature(s)

This document has been signed electronically in compliance with IQVIA and IQVIA Companies' electronic signature policies and procedures. This page is a manifestation of the electronic signatures, which may be confirmed within the IQVIA and IQVIA Companies' source system in accordance with IQVIA and IQVIA Companies' records retention policies.

Note: the Title field in the signature block has been intentionally left blank.

UserName: [name] (q103807)

Title:

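### Under the SAP's own treatment coding, the Appendix 3 primary MMRM code swaps the arm labels and reverses the sign of the Week 6 treatment difference

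*SAP*

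**What the plan says.** The variable table in SAP Appendix 3 defines the planned treatment as numeric, "TRT01PN (1=' SEP-36385 25, 50 or 75 mg/day'; 2='Placebo", and the visit as "AVISITN (4='Week 2'; 5='Week 3'; 6='Week 5'; 7='Week 6". In numeric order, treatment level 1 is SEP-363856, level 2 is placebo, and visit level 4 is Week 6.

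The primary MMRM block declares "CLASS SUBJID TRT01PN AVISITN" and shows no format and no ordering option. Its Week 6 arm means are "SEP-363856 at Week 6' [1, 2 4] / E CL" and "Placebo at Week 6' [1, 1 4] / E CL". Its Week 6 difference is "SEP-363856 vs Placebo at Week 6' [1, 2 4] [-1, 1 4] / E CL". Weeks 2, 3 and 5 follow the same pattern.

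Step 3 of the pattern-mixture block in the same appendix refits the primary MMRM to each imputed dataset, with the same class variables and model effects. There SEP-363856 at Week 6 is `[1, 1 4]`, placebo is `[1, 2 4]`, and the difference is `[1, 1 4] [-1, 2 4]`. Step 3 of the tipping-point analysis reuses this code.

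SAP Section 15.1.3 states the hypothesis and the model in words, and that text does not contain the error. SAP Section 15.2.1.4 treats a fall in SAPS-PD as improvement.

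**The concern.** The code labels each arm's mean with the other arm's name and subtracts in the wrong direction, judged against the coding table printed directly above it. A real benefit would then appear as a positive SEP-363856 versus placebo difference, and a real harm as a negative one.

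Section 15.1.3 derives the between-group effect size from this difference and calls for a plot of the LS means, so both would inherit the fault. The same model is repeated for the hallucinations and delusions subscales, the complete-case analysis (15.1.4.5) and the per-protocol analysis (15.1.4.6). It is used in similar form for CGI-S, NPI and MMSE (15.2.3). Code copied from this block would carry the reversal into those outputs. The primary analysis would also point the opposite way from the pattern-mixture and tipping-point analyses that are meant to test its robustness.

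**Working it through.** No figure in the plan depends on this contrast, so there is none to reproduce. The check maps the indices to the coding and then evaluates both contrasts on one dataset.

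**Step 1: read the contrasts.** Each bracket is [coefficient, treatment level, visit level]. Let m(a) be the model mean change at Week 6 in arm a, with levels in ascending numeric order.

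- Primary block, labelled SEP-363856: `[1, 2 4]` = m(placebo)
- Primary block, labelled placebo: `[1, 1 4]` = m(SEP)
- Primary block, labelled SEP-363856 versus placebo: m(placebo) - m(SEP) = -[m(SEP) - m(placebo)]
- Pattern-mixture Step 3, same label: `[1, 1 4] [-1, 2 4]` = m(SEP) - m(placebo)

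The primary contrast is therefore exactly -1 times the intended one. At four visits this affects 2 x 4 = 8 arm means and 4 differences. The variance of a contrast does not change when the contrast is multiplied by -1. The standard error, the absolute t statistic and the two-sided p-value stay the same, and the confidence limits change sign and swap places.

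**Step 2: see whether any one coding rescues the appendix.** What each part implies about TRT01PN level or value 1:

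| Part of Appendix 3 | Level or value 1 is |
|---|---|
| Variable table | SEP-363856 |
| Primary MMRM estimates | placebo |
| Pattern-mixture Step 2, "MNAR model (SAPS-PD7/model0bs=(TRT01PN='1" | placebo, because Section 15.1.4.2 restricts the imputation model to placebo data |
| Pattern-mixture Step 3 estimates | SEP-363856 |
| Tipping-point Step 2, "MNAR adjust (SAPS-PD7/delta=xx adjustobs=(TRT01PN ='1" | SEP-363856, the arm that is to receive the delta |

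- If 1 is SEP-363856, as stated, the primary block is reversed, while Step 3 and the tipping-point selector are right.
- If 1 is placebo, the primary block is right, but Step 3 is reversed and the delta falls on placebo subjects.
- If a text format made placebo sort first, the primary block would be right and Step 3 reversed. With the leading blank that the SAP prints in the SEP label, SEP would still sort first.

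No single ordering makes the primary block and Step 3 both right.

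**Step 3: numerical illustration.** One dataset was simulated with 24 SEP-363856 and 12 placebo subjects, four visits and a true Week 6 difference of -3. This value is assumed and does not come from the documents. The fit used a random-intercept mixed model with normal-based inference. It checks the algebra only and is not a run of the SAP's unstructured Kenward-Roger model.

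| Week 6 quantity | Primary block as printed | Indices exchanged |
|---|---|---|
| Labelled SEP-363856 | -2.08 | -5.79 |
| Labelled placebo | -5.79 | -2.08 |
| Labelled difference | -2.08 - (-5.79) = +3.71 | -5.79 - (-2.08) = -3.71 |
| 95% CI | 0.99 to 6.43 | -6.43 to -0.99 |
| SE | 1.39 | 1.39 |
| Two-sided p | 0.0075 | 0.0075 |

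The size of 3.71 belongs to the simulated data. The exact reversal holds for any data.

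**The case against.** The best case on the other side has three parts.

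**Direction.** The reversal in the primary block depends on the dataset following the printed coding and sorting numerically. Pattern-mixture Step 2 also treats value 1 as placebo, so the appendix may mix two conventions, and the table may be the part that is wrong. Editing the primary block without checking could then create the fault it is meant to cure. This stands as a reason to confirm the dataset coding first. It does not remove the contradiction, which holds under any ordering. Numeric order is also the natural reading of a variable that is called numeric and has no format shown.

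**Template code.** Dataset names, the baseline variable and delta are placeholders, so the code cannot run unedited, and Section 15.1.3 is correct in words. That is true, but the level indices are hard-coded and nothing prompts a programmer to revisit them.

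**Detection.** The descriptive summaries by arm and visit (Section 15), the LOCF ANCOVA (15.1.4.4) and the contrast coefficients that the code itself requests could all expose the swap, and the two-sided test decision is unaffected. This lowers the chance that a wrong sign survives to the report. It is not a reason to leave the wrong sign in the prespecified primary code, and noticing the conflict only after unblinding would mean changing the sign of the primary result once it is known.

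**Conclusion.** The point holds. Under the coding that the SAP prints, the primary MMRM code reports placebo minus SEP-363856 under a SEP-363856 versus placebo label at all four visits, and it swaps all eight arm means. The sign of the difference, its confidence limits and the between-group effect size are reversed, while the standard error and the two-sided p-value are unchanged. The direction of the fault rests on one assumption, that treatment levels sort by the stated numeric code. The conflict between the primary block and pattern-mixture Step 3 does not rest on it. The error is confined to Appendix 3, and the hypothesis and model in Section 15.1.3 are sound.

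**What to change.** 1. Confirm how TRT01PN is coded in the analysis dataset.
2. If it is coded as printed, use level 1 for SEP-363856 and level 2 for placebo throughout the primary block. The Week 6 contrast becomes `[1, 1 4] [-1, 2 4]`, with visit indices 1, 2 and 3 for Weeks 2, 3 and 5. In the same edit, change the pattern-mixture Step 2 selector to 2, so that the imputation model is estimated from placebo subjects. That selector is a separate defect, and it would alter estimates as well as labels.
3. If the dataset instead has 1 as placebo, correct the variable table, pattern-mixture Step 3 and the tipping-point selector, and leave the primary block as it is.
4. In either case add ORDER=INTERNAL to each model call and use one convention in every block.

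The cost is a few lines of SAP code, with no effect on data collection or sample size. The change should be made before the double-blind database is unblinded. If that point has passed, it should be described and justified in the final report, as SAP Section 19 requires.
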